10.3.3. Female Subjects of Childbearing Potential

A female subject is considered of childbearing potential (WOCBP) if she is not post-menopausal, not congenitally sterile; not diagnosed as infertile (and not undergoing treatment to reverse infertility); or has not undergone successful surgical sterilization (such as tubal ligation, bilateral oophorectomy, or hysterectomy) completed at least 3 months prior to Screening. A woman is considered of non-childbearing potential if she is post-menopausal (if she is either amenorrheal for greater than 2 consecutive years, or naturally post-menopausal [no mense] for at least 1 year), surgically sterile (tubal ligation, bilateral oophorectomy, or hysterectomy), congenital sterility, or diagnosed as infertile and not undergoing treatment to reverse infertility.

WOCBP must use effective methods of birth control starting at least one month prior to the Medical Screening Visit 1a and until the last study procedure, such as total abstinence, hormonal or non-hormonal intrauterine device, a double-barrier method (Condom and diaphragm or cervical cap with spermicide (foam, cream, gel, sponge)), oral, transdermal, injected or implanted or hormonal contraceptive. A sterile sexual partner is not considered an adequate form of birth control. Subjects on hormonal contraceptives must have been on the same hormonal contraceptive for at least one month before the Screening Visit 1 and continue throughout the duration of the study.

WOCBP will be instructed to contact the Investigator immediately if they suspect they might be pregnant.

10.3.4. Male Subjects

Male subjects must commit to not father a child or donate sperm from the first dose until the last dose.

Male subjects (with female partners of childbearing potential) must commit to the consistent and correct use of at least two effective methods of birth control (as listed below) or total abstinence from the Medical Screening Visit 1a until the last administration of the investigational product.

- Condom and diaphragm with spermicide (foam, cream, gel, sponge)
- Condom and cervical cap with spermicide (foam, cream, gel, sponge)
- Hormonal or non-hormonal intrauterine device (IUD)

Female partner(s) of male volunteers also have the option to use the following highly effective hormonal method of contraception: oral, transdermal, implants, injectables contraceptives.

11. STUDY PRODUCT AND TREATMENT SEQUENCE

11.1. Study Product and Treatment

The following products will be used in the study:

Product A: 0.25% Reproxalap Ophthalmic Solution (reproxalap) (Manufactured by Aldeyra Therapeutics, Inc.).

Product B: Vehicle Ophthalmic Solution (vehicle) (Manufactured by Aldeyra Therapeutics, Inc.)

Study treatment (reproxalap or vehicle) will be dosed topically in both eyes (1 drop in each eye). Study treatment will be administered 4 times (Dose 1, Dose 2 [3 hours post dose 1], Dose 3 [30 min post Dose 2] and Dose 4 [30 min post Dose 3] at Visit 2 and Visit 4. Study treatment will be administered 2 times (Dose 1 [administered approximately 5 min Prior to DEC entry] and Dose 2 [administered approximately 45 min into the DEC session]) at Visit 3 and Visit 5.

11.2. Treatment Sequence

The sequence in which subjects receive investigational product (reproxalap or vehicle) will be determined by randomization. [REDACTED]

[REDACTED] Randomization of subjects to one of the treatment sequences will be based on the randomization scheme.

Subjects will be randomized to one of the two sequences: AB or BA.

Sequence	Treatment Period 1	Treatment Period 2
AB	Reproxalap	Vehicle
BA	Vehicle	Reproxalap

11.3. Masking and Unmasking

11.3.1. Masking

This is a double-masked clinical trial. The Sponsor, Investigators, qualified site personnel (except delegated unmasked pharmacy staff), and subjects will be masked to the investigational product administered until database lock. Only the delegated unmasked pharmacy staff and Scientific Affairs staff involved with preparing the assignment of Treatment A and B to the sequence will have access to the treatment under evaluation.

11.3.2. Emergency Unmasking

Emergency unmasking should only be performed when necessary to treat the subject. Most often, knowledge of the possible treatment assignments is sufficient to treat a clinical trial subject who presents with an emergency condition.

The investigator should make every effort to contact the Medical Monitor to discuss the subject's emergency and the need to unmask prior to unmasking any subject.

In situations in which the investigator has tried but is unable to reach the Medical Monitor, best judgement on the part of the investigator should be used, based on the nature and urgency of the clinical situation, and may proceed with unmasking without having successfully reached and discussed the situation with the Medical Monitor. Once a subject's treatment assignment has been

unmasked, the Medical Monitor should be notified within 24 hours of the unmasking of the treatment, without revealing the treatment.

Emergency unmasking envelopes (one envelope for each subject) will be prepared and verified by unmasked pharmacy staff using the randomization scheme. To facilitate emergency unmasking and ensure subject safety, the unmasking envelopes will be kept in a secured area with access limited to Pharmacy staff, the PI and other key designated study staff. Unmasking will be performed by breaking the seal of the envelope, for that specific subject of interest only, and retrieving the treatment code.

The name of the unmasking person, the reason for unmasking, the subject randomization number, and the date and time of unmasking will be documented and confirmed by a signature. The reasons for and the date of unmasking must also be documented in the subject source document and the eCRF (if applicable).

Any AE or Serious Adverse Event (SAE) associated with breaking the mask must be recorded and reported as specified in the protocol. The investigator has the responsibility to contact the Sponsor in the event of a drug-related, serious, unexpected AE, [REDACTED] or designee will be provided with the treatment assignment for the subject for regulatory reporting.

If treatment assignment is unmasked, the treatment will be discontinued immediately, and the subject will be discontinued from the clinical trial.

The mask may be broken in the case of pregnancy should the subject desire this information.

12. STUDY VISITS

12.1. COVID-19 Screening

The following procedures will be performed as part of COVID-19 screening at each clinical visit:

- Subjects will be pre-screened based on a COVID-19 questionnaire.
- Body temperature will be measured.
- A nasal swab will be collected for COVID-19 rapid testing at the beginning of each study visit except Visit 3 and 5 ([Section 13.2.5](#)).

Subject's further participation in the study will be based on the COVID-19 test results and procedures.

12.2. Visit 1a: Medical Screening (Day -21 to -8)

The following activities will be completed at Visit 1a:

- A government-issued ID containing an image of the subject or a government-issued non-photo ID with a non-government photo ID of the subject will be used to confirm the subject's identification at every visit.
- Subjects will be asked to sign and date the Informed Consent Form.
- Demographic data, including date of birth, gender, race, ethnicity, height and weight will be recorded.

- Medical/Medication and Ocular history will be completed for each subject ([Section 13.2.6](#)).
- Corneal fluorescein staining will be performed and evaluated using the [\[REDACTED\]](#) ([Section 13.2.1](#)).
- A urine pregnancy test will be performed (for all female subjects). Subjects with a positive result will be excluded.
- The subjects will be evaluated for study inclusion, exclusion, and restriction criteria. Eligible subject will be scheduled to return for Visit 1b.

12.3. Visit 1b: DEC Screening (Day -14 to -7)

- The subjects will be evaluated for study inclusion, exclusion and restriction criteria.
- Medical/medication will be updated for each subject.
- An SVA and SLE will be performed pre- and post-DEC ([Section 13.2.2](#) and [13.2.3](#)).
- IOP will be performed post-DEC ([Section 13.2.4](#)).
- [\[REDACTED\]](#) training will be provided to the study participants.
- Schirmer's test (baseline) will be performed prior to vehicle administration before DEC entry ([Section 13.1.2](#)).
- Vehicle will be administered in the clinic approximately 5 minutes prior to the DEC entry and 45 minutes after DEC entry.
- Subjects will be exposed to a DEC session (approximately 90 minutes)
- Staff-assessed conjunctival redness will be performed approximately -10 and -5 minutes pre-DEC entry and approximately at 10, 20, 30, 40, 55, 65, 75, 85 and 90 minutes while in the DEC ([Section 13.1.1](#) and [Table 6-2](#)). Conjunctival redness will also be performed post-DEC (1 time)
- Ocular itching score and VAS ocular symptoms (dryness, discomfort, burning, grittiness and stinging) will be assessed pre- and post-DEC.
- VAS assessments for ocular symptoms (dryness, discomfort, burning, grittiness and stinging) will be performed approximately -12 and -7 minutes prior to DEC entry (and pre-vehicle administration) and approximately at 12, 22, 32, 42, 57, 67, 77, 87 and 92 minutes while in the chamber ([Section 13.1.3](#) and [Table 6-3](#)).
- Adverse events and concomitants medications will be recorded during the visit.

12.4. Visits 2 – Randomization and Baseline Treatment Visit

Eligible subjects will return to clinic for the first treatment visit approximately 7 to 14 days after Visit 1b. The following activities will be performed:

- Medical/medication will be updated for each subject.
- The subjects will be evaluated for study inclusion, exclusion and restriction criteria.

- A urine pregnancy test will be performed (for all female subjects). Subjects with a positive result will be excluded.
- Subjects will be randomized to study treatments sequence (AB or BA) ([Section 11.2](#)).
- Study treatment will be administered 4 times as follows: Dose 1, Dose 2 (3 hours post dose 1), Dose 3 (30 min post Dose 2) and Dose 4 (30 min post Dose 3).
- Staff-assessed conjunctival redness, ocular itching score and VAS ocular symptoms (dryness, discomfort, burning, grittiness and stinging) will be performed at pre-dose and approximately 10 (+2) minutes after Dose 1, 2 and 3. ([Section 13.1.3 to 13.1.8](#)).
- Schirmer's test will be performed approximately 10 (+2) minutes pre-Dose 4 and approximately 5 (+2) minutes post-Dose 4 ([Section 13.1.2](#)).
- Adverse events and concomitants medications will be recorded during the visit.
- Subjects will return to clinic the following day.

12.5. Visits 3 – DEC Treatment Visit

The following activities will be performed at Visit 3:

- Medical/medication will be updated for each subject.
- The subjects will be evaluated for study inclusion, exclusion and restriction criteria.
- [REDACTED] will be repeated for the study participants.
- IOP will be performed post-DEC ([Section 13.2.4](#)).
- An SVA and SLE will be performed pre- and post-DEC. Pre-DEC SVA and SLE will be performed prior to symptom assessment ([Section 13.2.2](#) and [13.2.3](#)).
- Treatment (same as Visit 2) will be administered in the clinic 2 times as follows: Dose 1 (administered approximately 5 min prior to DEC entry), Dose 2 (administered approximately 45 min into the DEC session).
- Subjects will be exposed to a DEC session (approximately 90 minutes).
- Staff-assessed conjunctival redness will be performed approximately -10 (+1) and -5 (+1) minutes prior to DEC entry (and pre-treatment administration) and approximately at 10, 20, 30, 40, 55, 65, 75, 85 and 90 minutes while in the DEC ([Section 13.1.1](#) and [Table 6-2](#)). Conjunctival redness will also be performed post-DEC (1 time).
- Ocular itching score and VAS ocular symptoms (dryness, discomfort, burning, grittiness and stinging) will be assessed pre- and post-DEC.
- VAS assessments for ocular symptoms (dryness, discomfort, burning, grittiness and stinging) will be performed approximately -12 (+1) and -7 (+1) minutes prior to DEC entry (and pre-treatment administration) and approximately at 12, 22, 32, 42, 57, 67, 77, 87 and 92 minutes while in the chamber ([Section 13.1.3](#) and [Table 6-3](#)).
- Adverse events and concomitants medications will be recorded during the visit.

12.6. Visit 4 - Baseline Treatment Visit

Subjects will return to Visit 4 after 7 to 14 days of Visit 3, and undergo the same procedures as Visit 2.

12.7. Visit 5 – DEC Treatment Visit

- Subjects will return to Visit 5 and undergo the same procedures as Visit 3.
- Study exit

12.8. Follow-up Phone call follow-up

For any subjects who withdraw/withdrawn prior to study exit, there will be a phone call within 7(+3) days after they withdraw to follow up on the subject's health.

13. STUDY ASSESSMENTS AND PROCEDURES**13.1. Efficacy Assessments**

For details regarding visits and timing of assessments and procedures, refer to [Section 6](#).

[figure not shown]

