9. STUDY DESIGN

9.1. Overall Study Design

[figure not shown]
This is a randomized, double-masked, vehicle-controlled, crossover clinical trial to assess efficacy and safety of 0.25% reproxalap ophthalmic solution compared to vehicle in subjects with dry eye disease in a DEC.

This clinical trial will include 6 visits, 2 in the Screening period (Visit 1a for medical screening and Visit 1b for DEC screening) and 4 visits in the Treatment periods. The first treatment period (Visit 2 and 3) will begin after at least a 7 to 14 days of wash out period post-screening Visit 1b. At Visit 2, subjects will be randomized to determine the order in which they will receive Reproxalap and vehicle treatment. Subjects will receive the same study treatment at Visit 2 (4 times) and Visit 3 (2 times), which will be scheduled on consecutive days. After a washout period of 7 to 14 days subjects will return to the clinic for Treatment period 2 (Visit 4 and 5) and cross over to receive the other treatment at Visit 4 (4 times) and Visit 5 (2 times) scheduled on consecutive days.

Visit 2 and Visit 4 will not include DEC exposure. Schirmer's test will be conducted at these visits. Visit 3 and Visit 5 will include DEC exposure and assessment of symptoms before, and during exposure to DEC). Conjunctival redness will be assessed by trained study staff, whereas ocular dryness, itching, discomfort, burning, grittiness and stinging will be separately assessed by subjects [REDACTED].

Safety endpoint assessments will be performed throughout the study. Adverse events and concomitant medication will be recorded at each visit.

Figure 9-1 Study Design

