13.2.7. Adverse Event Query/Concomitant Medication Query

The staff will record all adverse events observed, queried, or spontaneously volunteered by the subjects. An adverse event query will be performed as scheduled as per Investigator's direction throughout the post-dose confinement period, prior to being released from confinement, and at each return visit for the study (if applicable). Subjects will be asked non-leading questions such as "How do you feel now?", "How have you felt since last asked?" or "Have you taken any

medication since last asked?" If the presence of any symptom(s), adverse event(s), and/or concomitant medication is recorded, the clinical staff may advise the subjects to remain at the clinic site for safety reasons until the Investigator decides it is safe for the subjects to leave. If the subject decides to leave despite the Investigator's advice, he/she will be asked to sign a waiver.

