#### 17. Safety Analysis

All safety analyses will be conducted using the safety population.

An AE is defined as any untoward medical occurrence associated with the use of an IP in humans, whether or not considered IP-related. An AE can be any unfavorable and unintended sign (e.g., an abnormal laboratory finding), symptom, or disease temporally associated with the use of an IP, without any judgment about causality.

14-JUN-2022

Confidential & Proprietary

Treatment-emergent adverse events (TEAEs) are defined as any adverse event that occurs or worsens after the first dose of study treatment. AEs recorded in the eCRF which began prior to treatment will not be included in the summary tables but will be included in the AE data listings.

An overall summary will display the number of subjects who experience one or more AEs in each of the following categories:

- All TEAEs regardless of severity or presumed relationship to Study Intervention
- Treatment-Emergent AEs judged related to Study Intervention
- Treatment-Emergent Severe Adverse Events
- Treatment-Emergent Severe Adverse Events judged related to Study Intervention
- Treatment-Emergent Serious Adverse Events
- Treatment-Emergent Serious Adverse Events judged related to Study Intervention
- Treatment-Emergent Adverse Events with Fatal Outcome
- Treatment-Emergent Adverse Events with Fatal Outcome judged related to Study
  Intervention
- Treatment-Emergent Adverse Events leading to Withdrawal from the Study
- Treatment-Emergent Adverse Events leading to Withdrawal from the Study judged related to Study Intervention

The number of emergent events and the number and percentage of subjects with TEAEs will be summarized by treatment-period. SOC and PT for different categories of TEAEs. At each level of tabulation (e.g., at the PT level) subjects will be counted only once if they had more than one such event reported during the AE collection period.

The following summary tables will be presented for TEAE data:

- Treatment-Emergent Adverse Events Overview
- Treatment-Emergent Adverse Events, by Severity and Grade
- Treatment-Emergent Adverse Events, by SOC and PT
- Treatment-Emergent Severe Adverse Events, by SOC and PT
- Treatment-Emergent Serious Adverse Events, by SOC and PT
- Treatment-Emergent Adverse Events with Fatal Outcome, by SOC and PT

- Treatment-Emergent Adverse Events leading to Withdrawal from the Study, by SOC and PT
- Treatment-Emergent Drug Related Adverse Events, by SOC and PT

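### Completers have no scheduled adverse-event contact after leaving Visit 5, about an hour after the last dose, so delayed events after Period 2 dosing are not solicited

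*Protocol*

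**What the plan says.** Each treatment period has two visits on consecutive days. Protocol 9.1 says of Period 1: "Subjects will receive the same study treatment at Visit 2 (4 times) and Visit 3 (2 times), which will be scheduled on consecutive days". It schedules Visits 4 and 5 the same way.

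Protocol 12.6 then sets the gap between periods: "Subjects will return to Visit 4 after 7 to 14 days of Visit 3, and undergo the same procedures as Visit 2". The Visit 2 procedures in Protocol 12.4 include recording adverse events (AEs). Under Protocol 13.2.7, AE queries are made during post-dose confinement, "prior to being released from confinement, and at each return visit for the study". An event that starts at home after Visit 3 can therefore be reported at Visit 4.

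Period 2 has no equivalent. Protocol 12.7 says: "Subjects will return to Visit 5 and undergo the same procedures as Visit 3", and then lists study exit. The only later contact is in Protocol 12.8: "For any subjects who withdraw/withdrawn prior to study exit, there will be a phone call within 7(+3) days after they withdraw". That excludes completers.

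SAP 17 counts as treatment-emergent (TEAE) any event that starts or worsens after the first dose of study treatment. The counts and percentages of subjects with TEAEs "will be summarized by treatment-period". The visible text gives no end date for a period and no rule for events that start in the washout. The exposure formula in SAP 15.2 runs from Visit 2 to completion, across both treatments and the washout, so it gives no per-period denominator.

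**The concern.** The AE query is a listed safety endpoint (Protocol 8.2.3), and in a crossover each treatment is given to about half the subjects in the period with the short follow-up. Two things are at stake.

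- **Detection.** A reaction that starts after release from the second visit of a period can be solicited only in subjects who had that treatment in Period 1. Completers also get less scheduled contact after their last dose than subjects who withdraw.
- **Presentation.** If washout-onset events are counted in Period 1, that column covers a week or two and the Period 2 column two days. Period 2 would then show fewer events for a reason unrelated to treatment.

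**Working it through.** **Step 1: is any time planned after Visit 5?** The stated duration is about 19 to 39 days (Protocol 5, SAP 5.1). Visit 1a falls on Day -21 to -8, there is no Day 0, and Visits 2 and 3 are Days 1 and 2.

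- Taking 7 to 14 as clear days between Visits 3 and 4 (which fits the SAP's planned Day 10), Visit 4 is Day 10 to 17 and Visit 5 is Day 11 to 18. The total is 8 + 11 = 19 to 21 + 18 = 39 days, an exact match.
- Taking 7 to 14 as a difference in dates, Visit 5 is Day 10 to 17, and the total is 8 + 10 = 18 to 21 + 17 = 38 days, or 19 to 39 if a Day 0 is counted.

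On either reading the stated duration ends at Visit 5. The body of the schedule of assessments (Protocol Table 6-1) is not visible in the public copy, but Protocol 12.7 also places exit at Visit 5.

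**Step 2: observation windows.**

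- Period 1, Visit 2 to Visit 4: 1 + 7 = 8 to 1 + 14 = 15 elapsed days (9 to 16 on the clear-days reading; 10 - 1 = 9 on the SAP's planned days).
- Period 2, Visit 4 to Visit 5: 1 elapsed day, or 2 calendar days.
- After the last dose, given about 45 minutes into a session of about 90 minutes: 90 - 45 = 45 minutes, or 90 + 15 - 45 = 60 minutes to the end of the post-chamber redness window.

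**Step 3: chance of seeing a delayed event.** SAP 7 gives about 25 subjects per sequence, 50 in all. (Protocol 15.2 gives about 50 per sequence with 50 randomized in total; the Period 2 share is one half either way.) Take an event that starts only after the second visit of a period, and assume the Visit 4 query catches every Period 1 case. The chance of at least one case among n observable exposures is 1 - (1 - p)^n. The documents give no incidence p, so a range is assumed.

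| Assumed incidence | n = 25 | n = 50 |
|---|---|---|
| 1% | 1 - 0.99^25 = 22% | 1 - 0.99^50 = 39% |
| 5% | 1 - 0.95^25 = 72% | 1 - 0.95^50 = 92% |
| 10% | 1 - 0.90^25 = 93% | 1 - 0.90^50 = 99.5% |

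With no cases seen, the one-sided 95% upper bound on the rate is 1 - 0.05^(1/n): 11.3% for n = 25 and 5.8% for n = 50.

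**Step 4: the by-period table, if washout-onset events go to Period 1.** On the date-difference reading, in calendar days with 25 subjects per cell:

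- Period 1 cell: 25 × 8 = 200 to 25 × 15 = 375 subject-days. Period 2 cell: 25 × 2 = 50. The ratio is 4.0 to 7.5.
- Expected events at an assumed constant daily rate, Period 1 versus Period 2: 1.0 to 1.9 versus 0.25 at 0.5%; 2.0 to 3.75 versus 0.5 at 1%; 4.0 to 7.5 versus 1.0 at 2%.

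**Step 5: reproxalap against vehicle.** Within a period both treatments have the same window. Pooled over equal sequences, each has 200 + 50 = 250 to 375 + 50 = 425 subject-days. A 27/23 split shifts this only to 262 versus 238, up to 451 versus 399.

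**The case against.** The strongest reply is that no treatment comparison is harmed, and Step 5 bears that out. A reader might infer that the design favours reproxalap or counts against it. It does neither, because half of the vehicle exposures are cut short in the same way.

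A reader might also infer that Period 2 exposures go unobserved after dosing. That is not so. The last dose is followed by about 45 to 60 minutes on site, with visual acuity, slit-lamp and pressure checks after the chamber and an AE query before release. Four of the six Period 2 doses are given at Visit 4 and are followed by a full visit the next day, so a reaction within about a day of those doses can be seen in either sequence. Recorded AEs are followed to resolution or stabilization (Protocol 18.3.1). What is missing is solicitation of events that start after release from Visit 5.

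Third, the unequal table windows are conditional. The SAP does not say that washout-onset events belong to Period 1, and it plans no test of one period against the other. The documented gap is the absence of a visible assignment rule.

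Finally, the study objective is efficacy, dosing is brief, safety analysis is descriptive, and Protocol 7.1 cites more than 1200 exposed subjects without clinically significant safety concerns. Period 1 follow-up is also modest: a recall query at Visit 4, with staff available for queries in between (Protocol 18.1), and no eye examination among the listed Visit 4 procedures. These points limit the importance of the gap but do not close it.

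**Conclusion.** The point holds as a gap in detecting delayed events, and it is minor. AEs that start after release from Visit 5 are not solicited in the roughly 25 of 50 subjects who receive reproxalap in Period 2, nor in those who receive vehicle then. For such events the observable exposures per treatment fall from about 50 to about 25, which nearly doubles the upper bound after a zero count. The loss in detection probability is about 17 to 20 percentage points at assumed incidences of 1% to 5% and about 7 points at 10%.

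These figures assume that the event starts only after the second visit of a period and that Visit 4 recall is complete; less complete recall would lower the number observable in Period 1 as well. The loss of comparability between periods is a separate, conditional point that depends on how washout-onset events are assigned. The documents do not support a claim of bias between treatments.

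**What to change.** - **Protocol 12.8:** extend the existing 7(+3)-day phone call to completers, timed from Visit 5, as an AE data-collection contact. The Period 2 window becomes 1 + 7 = 8 to 1 + 10 = 11 elapsed days, against 8 to 15 in Period 1. The cost is about 50 short calls, and last contact moves 7 to 10 days later.
- **SAP 17:** when TEAEs are presented by treatment-period, use a common window for both periods, from the first dose of the period to release from its second visit. Assign washout-onset events to the preceding treatment and show them separately; events reported at the new call can be shown in the same way. This costs only wording. It makes the period columns comparable, but without the call it recovers no unseen events.
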